9 STATISTICAL CONSIDERATIONS

A statistical analysis plan (SAP) will be finalized prior to unblinding the patients' treatment assignments and will provide further details regarding the definition of analysis endpoints and analysis methodology to address all study objectives. Changes made to the data analysis methods as described in the protocol will be documented in the SAP and will not necessitate a protocol amendment. All departures from the statistical analyses described in the approved protocol, whether made before or after unblinding, will be documented, and justified in the final clinical study report.

The study randomized 100 patients with Bipolar Disorder (Bipolar I or Bipolar II) before Amendment 2.0 (dated 02 Nov 2020). The efficacy data of these 100 patients will be combined with those of patients with Bipolar Disorder enrolled after Amendment 2.0 as a separate analysis.

Table 9-1 presents an overview of the statistical data analyses planned for all patients enrolled in the study.

Table 9-1: Overview of Statistical Data Analyses

	Patients	Patients Randomized after Protocol Amendment 2.0			All Bipolar Patients	All Patients
Analysis	Randomized before Protocol Amendment 2.0	Bipolar Disorder with Mixed Features	MDD with Mixed Features	All Patients Randomized after Protocol Amendment 2.0	(randomized before or after Amendment 2.0)	randomized before or after Amendment 2.0
Patient Disposition	Yes	Yes	Yes	Yes	Yes	Yes
Protocol Deviation	Yes	Yes	Yes	Yes		Yes
Demographic and baseline characteristics	Yes	Yes	Yes	Yes	Yes	Yes
Bipolar Diagnosis, Psychiatric Diagnosis and History	Yes	Yes	Yes	Yes	_	_
Medical History	Yes	Yes	Yes	Yes	—	—
Prior/Concomitant Medication	Yes	Yes	Yes	Yes	—	_
Exposure/ Compliance	Yes	Yes	Yes	Yes	Yes	Yes
Primary and Key Secondary Efficacy	Yes ¹	Yes	Yes	Yes	Yes	Yes
AE	Yes	Yes	Yes	Yes	Yes	Yes
Labs	—	Yes	Yes	Yes	Yes	Yes
Vital Signs		Yes	Yes	Yes	Yes	Yes
ECG	_	Yes	Yes	Yes	Yes	Yes
C-SSRS		Yes	Yes	Yes	Yes	Yes
YMRS	Yes	Yes	Yes	Yes	Yes	Yes
AIMS, BARS, and SAS ²		Yes	Yes	Yes	Yes	—

AE = adverse event; AIMS = Abnormal Involuntary Movement Scale; BARS = Barnes Akathisia Rating Scale; C-SSRS = Columbia Suicide Severity Rating Scale; ECG = electrocardiogram; SAS = Simpson-Angus Scale; YMRS = Young Mania Rating Scale.

¹ Descriptive statistics only.

² AIMS, BARS, and SAS assessments were added after implementation of Protocol Amendment 2.0.

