9.1 Sample Size Considerations

The assumed effect size (treatment group difference relative to pooled SD) of 0.37 for lumateperone is based on a treatment difference of 3.3 units with a common pooled SD of 9 for the primary efficacy parameter, change from baseline to Day 43 in MADRS total score. A sample size of 350 patients (175 per treatment group) will need to be enrolled after the implementation of Amendment 2.0 (dated 02 Nov 2020) to provide 90% power for primary analysis for the combined population of Bipolar Disorder with mixed features and MDD with mixed features based on an MMRM model using simulation method (Lu, 2012). The simulation assumed a correlation of 0.7 between the repeated measures and a dropout rate of 10% based on historical data.

The assumed values of drop-out rate of 10%, correlation of 0.7, and standard deviation of 9 are approximate estimates from a previous successful study of lumateperone for bipolar depression. The assumed treatment difference of 3.3 used to obtain the power of 90% is considered appropriate as the generated sample size can cover a wide range of clinically relevant treatment difference to be detected as statistically significant.

The study will enroll approximately equal number of patients (175) for the Bipolar Disorder with mixed features and for MDD with mixed features following Amendment 2.0. Assuming an effect size of 0.45, and same assumptions of drop-out rate and correlation between the repeated measures, this sample size (approximately 87 patients in each treatment group) for each of the two subpopulations is expected to provide approximately 80% statistical power for the primary efficacy analysis with the adjustment of multiplicity for the testing of the primary analysis in each of the subpopulations.

The study randomized approximately 100 patients under the original protocol before the implementation of Amendment 2.0 (dated 02 Nov 2020); therefore, the total enrollment for the study will be approximately 450 patients.

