9.3 Analysis Sets

All Enrolled Set will contain all patients who signed the informed consent for the study.

All Patients Randomized Set will contain all patients who signed the informed consent and were randomized to study drug.

Intent-to-treat (ITT) Analysis Set will contain all randomized patients who received at least 1 dose of study drug and who had a non-missing (pre-dose) baseline assessment and at least 1 non-missing post-baseline assessment of MADRS total score.

Modified Intent-to-treat (mITT) Analysis Set will contain all randomized patients who received at least 1 dose of study drug and who had a valid (pre-dose) baseline assessment and at least 1 valid post-baseline assessment of MADRS total score and were enrolled after the implementation of Amendment 2.0 (dated 02 Nov 2020). Patients enrolled before the implementation of Amendment 2.0 will not be included in the mITT Analysis Set.

Sensitivity Set will contain all patients randomized after the implementation of Amendment 2.0 (dated 02 Nov 2020) and who received at least 1 dose of study drug and who had a valid (pre-dose) baseline assessment of MADRS total score. Patients enrolled before the implementation of Amendment 2.0 will not be included in the Sensitivity Set.

The Bipolar Intent-to-treat (bITT) Analysis Set will contain all randomized Bipolar Disorder patients who received at least 1 dose of study drug and had baseline assessment and at least 1 post-baseline assessment of MADRS total score. The bITT Analysis Set will be based on patients enrolled before the implementation of Amendment 2.0 as well as the patients of Bipolar Disorder with mixed features enrolled after the implementation of Amendment 2.0.Safety Analysis Set will contain all patients who received at least 1 dose of study drug.

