9.4 Statistical Analysis Methodology

Categorical variables (eg, AEs) will be summarized using the number and percentage of patients in specified categories. Unless otherwise stated, the calculation of percentages will be based on the number of patients in the analysis set of interest. Continuous variables (eg, MADRS total score) will be summarized using descriptive statistics including number of patients, mean, standard deviation, median, minimum, and maximum.

For analysis purposes, baseline is defined as the last non-missing measurement before the first dose of study drug. Assessments on Day 1 for which times are recorded will be

considered baseline if the assessment time is before the time of the first dose of study drug.

Unless stated otherwise, statistical tests will be performed at a 2-sided significance level of 0.05, leading to 95% (2-sided) confidence intervals (CIs).

For efficacy analyses in which study site is a factor, a small site will be defined as a site with less than 2 patients in at least one treatment group for each specific analysis set (ie, the mITT Set, the Bipolar Disorder with mixed features based on mITT Set, the MDD with mixed feature based on mITT Set, and the bITT Set). Small sites in each specific analysis set will be pooled to form pseudo-sites so that each treatment group includes at least 2 patients within the site. Pooling will be performed separately for each analysis set but using the same algorithm described as the following:

Based on the number of patients, small sites will be ordered from the largest to the smallest, and sites of the same size will be ordered from the largest site code to the smallest site code. The pooling process starts with the largest small site from the top, which will be pooled with the smallest from the bottom until a non-small site is formed. The process will be repeated using the small sites left out after the first pass. If any sites are left out at the end of the process, they will be pooled with the smallest pseudo site. If there is more than 1 smallest pseudo site, the pseudo site with the smallest site code will be selected. In case the pseudo site formed by pooling all small sites is still a small site, it will be pooled with the smallest non-small site. If there is more than 1 smallest non-small site. If there is more than 1 smallest non-small site. If there is more than 1 smallest non-small site.

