This study was originally designed as a Phase 3, randomized, double-blind, placebo-controlled, multicenter study to evaluate the efficacy and safety of lumateperone as monotherapy in the treatment of patients with Major Depressive Episodes (MDEs) associated with bipolar I or bipolar II disorder. After the study started, Study ITI-007-402 (a Phase 3, randomized, double-blind, placebo-controlled, multicenter study to evaluate the efficacy and safety of lumateperone adjunctive to lithium or valproate in the treatment of patients with MDEs associated with bipolar I or bipolar II disorder) reported its results and demonstrated lumateperone successfully reduced MDEs associated symptoms based on treatment difference in change from baseline to Day 43 in MADRS total score for lumateperone vs placebo. As a result, there was no need for an additional pivotal study for the treatment of patients with MDEs associated with bipolar II disorder.

Therefore, Study ITI-007-403 was repositioned for the treatment of patients with MDEs associated with bipolar disorder with mixed features or major depressive disorder (MDD) with mixed features. This change was described in Protocol Amendment 2.0 (dated 02 Nov 2020). A total of 100 patients had been randomized under the original protocol before the implementation of Protocol Amendment 2.0. Protocol Amendment 2.0 plans for an additional enrollment of 350 patients with approximately equal number of patients for bipolar disorder with mixed features and for MDD with mixed features.

For data analysis, the main difference between the original protocol before Protocol Amendment 2.0 and after Protocol Amendment 2.0 is in the patient populations: Original Protocol before Protocol Amendment 2.0 enrolled patients with MDE associated with bipolar I or bipolar II disorder; while after Protocol Amendment 2.0, the study enrolled patients with MDEs associated with bipolar disorder with mixed features or MDD with mixed features.

Both the Original Protocol and Protocol Amendment 2.0 consist of the same study design of a Screening Period, Double-blind Treatment Period (DBTP), and a Safety Follow-up Period (SFUP) with the same planned assessments.

Screening Period (2 Weeks)

Potential patients will be evaluated during a Screening Period lasting up to 2 weeks unless an extension of the Screening Period is approved by the Medical Monitor or Sponsor Designee.

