8.2 Treatment Compliance

Dosing compliance for the DBTP is defined as the number of capsules actually taken by a patient during that phase divided by the number of capsules prescribed to be taken during the DBTP multiplied by 100. The total number of capsules actually taken during the DBTP is calculated as the sum of capsules taken during the DBTP as obtained from the study drug record. The number of capsules prescribed to be taken for the DBTP is calculated by multiplying the number of days in the DBTP by the number of capsules prescribed per day.

Descriptive statistics for study drug compliance will be presented by treatment group for the entire DBTP for the Safety Analysis Set as outlined in Table 2-2.

9. EFFICACY ANALYSES

All efficacy analyses will be performed in the following analysis sets: the mITT Analysis Set, the patients with bipolar disorder with mixed features in the mITT Analysis Set, the patients with MDD with mixed feature in the mITT Analysis Set, and the bITT Analysis Set. Baseline for efficacy parameters will be defined as the last non-missing efficacy measurement prior to the first dose of double-blind study drug. All statistical hypothesis tests will be performed at the 2-sided significance level of 5% for main effects. All confidence intervals (CIs) will be 2-sided 95% CIs, unless stated otherwise.

The efficacy analyses will be performed based on the treatment to which the patient is randomized regardless of the actual treatment received.

The efficacy analyses of MADRS assessments will be based on the rater-administered MADRS.

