9.1 Primary Efficacy Parameter

The primary efficacy parameter will be the change from baseline in MADRS total score at the end of Week 6 (Day 43). The MADRS contains 10 items that assess depression, with scores for each item ranging from 0 (absence of symptoms) to 6 (symptoms of maximum severity). The MADRS total score is the sum of the 10 individual items.

The primary efficacy analysis will be performed based on the mITT Analysis Set using the mixed model with repeated measures (MMRM) with terms for treatment, pooled study site, stratification variable (bipolar I, bipolar II, or MDD), visit, baseline, and treatment-by-visit and baseline-by-visit interactions. An unstructured covariance matrix will be used to model the covariance of within-patient scores. The Kenward-Roger approximation will be used to estimate denominator degrees of freedom (Kenward et al, 1997). This analysis will only use the observed post-baseline scores without imputation of missing values. The treatment difference for lumateperone 42 mg vs placebo will be estimated and reported along with the corresponding 95% CI and p-value.

In the case that the MMRM with unstructured covariance fails to converge then the Fisher scoring algorithm will be used to provide better initial values of the covariance parameters. In the rare event that model still does not converge after using those initial values, the following alternative structures will be attempted in the specified order until convergence is achieved: heterogeneous Toeplitz structure (TOEPH), heterogeneous autoregressive(1) (ARH(1)), heterogeneous compound symmetry (CSH), No Diagonal Factor Analytic (FA0(q), with q equal to the number of time points), Toeplitz structure (TOEP), autoregressive(1) (AR(1)), and compound symmetry (CS).

[figure not shown]
The primary efficacy analysis will also be performed based on subpopulation of patients associated with bipolar depression with mixed features and patients associated with MDD with mixed features in the mITT Analysis Set. The same MMRM described above will be applied to subpopulation of bipolar disorder and subpopulation of MDD without the stratification at screening as a factor.

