14.9.2 Incomplete Stop Date

The following rules will be applied to impute the missing numeric fields for an incomplete prior or concomitant medication stop date. If the imputed stop date is before the start date (imputed or non-imputed start date), the imputed stop date will be equal to the start date.

Missing month and day

- If the year of the incomplete stop date is the same as the year of the last dose of doubleblind study drug, the month and day of the last dose of double-blind study drug will be assigned to the missing fields
- If the year of the incomplete stop date is before the year of the last dose of double-blind study drug, *December 31* will be assigned to the missing fields
- If the year of the incomplete stop date is after the year of the last dose of double-blind study drug, *January 1* will be assigned to the missing fields

Missing month only

• If only the month is missing, the day will be treated as missing and both the month and the day will be replaced according to the above procedure

Missing day only

[figure not shown]
- If the month and year of the incomplete stop date are the same as the month and year of the last dose of double-blind study drug, the day of the last dose of double-blind study drug will be assigned to the missing day
- If either the year of the incomplete stop date is before the year of the date of the last dose of double-blind study drug or if both years are the same but the month of the incomplete stop date is before the month of the date of the last dose of double-blind study drug, the last day of the month will be assigned to the missing day

• If either the year of the incomplete stop date is after the year of the date of the last dose of double-blind study drug or if both years are the same but the month of the incomplete stop date is after the month of the date of the last dose of double-blind study drug, the first day of the month will be assigned to the missing day.

15. CHANGES TO ANALYSES SPECIFIED IN THE PROTOCOL

There are no changes to the analyses specified in the protocol.

	-	

17. REFERENCES

Lu K. Sample size calculations with multiplicity adjustment for longitudinal clinical trials with missing data. Statist Med. 2012; 31:19-28.

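### The supportive bITT analysis pools bipolar patients from before and after Amendment 2.0, but the only visible MMRM has no cohort factor and no estimate of the treatment effect by cohort

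*Protocol*

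**What the plan says.** **The pooling.** Protocol 9.3 defines the set: "The bITT Analysis Set will be based on patients enrolled before the implementation of Amendment 2.0 as well as the patients of Bipolar Disorder" (the latter being post-amendment and having mixed features). Protocol 9 gives the intent: "The efficacy data of these 100 patients will be combined with those of patients with Bipolar Disorder" enrolled after the amendment, as a separate analysis. Protocol 9.1 plans about 175 post-amendment bipolar patients.

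**The populations.** SAP 2 says that "the main difference between the original protocol before Protocol Amendment 2.0 and after Protocol Amendment 2.0 is in the patient populations". Before the amendment the study took major depressive episodes in bipolar I or II disorder; afterwards it required mixed features.

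**The analysis.** SAP 9 opens with "All efficacy analyses will be performed in the following analysis sets", and bITT is one of the four listed. Protocol 9.4 also names bITT among the sets for which sites are pooled. SAP 9.1 describes an MMRM "with terms for treatment, pooled study site, stratification variable (bipolar I, bipolar II, or MDD), visit, baseline", plus treatment-by-visit and baseline-by-visit interactions. Protocol 9.4.4 gives the same terms. Both sections present the model for the mITT set and its two diagnostic subpopulations; neither describes a bITT model. Cohort is not among the subgroups in SAP 9.3, which are run on mITT sets only.

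**What is reported by cohort.** Post-amendment bipolar patients get their own MMRM (SAP 9.1). Pre-amendment patients get descriptive MADRS and CGI-S results by treatment group at each assessment (SAP 9.3; Protocol Table 9-1, footnote 1).

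**What carries the conclusion.** The Protocol synopsis rests it on the mITT set, which excludes every pre-amendment patient.

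**The concern.** The two parts of bITT were recruited one after the other under different entry criteria, and the SAP itself names the population as the main difference between them. Cohort is therefore a known design factor in this set, and the visible model does not use it. Two modest consequences follow.

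- **Precision.** A cohort difference in mean MADRS change that site, stratum and baseline do not absorb goes into the residual, so the standard error is a little larger than it need be.
- **Interpretation.** The pooled estimate averages two treatment effects. Nothing visible gives a model-based effect for the pre-amendment cohort, or a between-cohort difference with an interval, to set beside it. A reader must compare an adjusted estimate for one cohort with raw means for the other.

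A documentation point sits beside this. Protocol Table 9-1 plans primary and key secondary efficacy for all patients randomised before or after the amendment, without the descriptive-only footnote. The sets listed in SAP 9 do not include that population, yet SAP 15 says "There are no changes to the analyses specified in the protocol".

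**Working it through.** **Inputs from the documents.** Difference and SD: "based on a treatment difference of 3.3 units with a common pooled SD of 9" (Protocol 9.1). Alpha: "statistical tests will be performed at a 2-sided significance level of 0.05" (Protocol 9.4). Dropout 10% (Protocol 9.1). Allocation 1:1 (Protocol 2.2), assumed also to hold before the amendment. Cohorts of 100 and about 175, so N = 275 and the pre-amendment share is p = 100/275 = 0.364.

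**Assumed, because the documents give no value.** The cohort difference in mean change, D, and any cohort-specific treatment effects.

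**1. The plan's own figure.** n per arm = 2 × (1.960 + 1.282)² × 81 / 3.3² = 156.3, so 157. Then 157/0.9 = 174.4, so 175 per arm and 350 in total, as stated. No sample size or power is stated for bITT.

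**2. bITT with no cohort difference.** Completers 0.9 × 275 = 247.5. SE = 9 × √(4/247.5) = 1.14. Power for 3.3 points = Φ(3.3/1.144 − 1.960) = 82.2%.

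**3. Cost of omitting cohort.** The residual variance becomes 81 + p(1−p)D², with p(1−p) = 0.231.

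| Assumed D (points) | Added variance | Added SE | bITT power for 3.3 points |
|---|---|---|---|
| 2 | 1.1% | 0.6% | 81.8% |
| 3 | 2.6% | 1.3% | 81.3% |
| 5 | 7.1% | 3.5% | 79.6% |
| 9 (one SD) | 23.1% | 11.0% | 73.9% |

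These are upper values, because pooled site and baseline MADRS would take up part of D.

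**4. Bias.** In 2,000 simulated trials of the Day 43 change (248 completers, equal arms within cohort, true benefit 3.3), the mean estimate was −3.29 both with and without a cohort term at D = 3 and at D = 5. Only the SE moved: 1.153 without against 1.139 with at D = 3, and 1.183 against 1.141 at D = 5.

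**5. What pooling does to unequal effects (illustrative).**

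- Effects of 5.0 before and 1.5 after pool to (100 × 5.0 + 175 × 1.5)/275 = 2.77 points, and z = 2.77/1.144 = 2.4. The post-amendment cohort alone has SE = 9 × √(4/157.5) = 1.43 and z = 1.5/1.43 = 1.0.
- Effects of 0 before and 4.05 after (0.45 × 9, the subpopulation effect size in Protocol 9.1) pool to 175 × 4.05/275 = 2.58 points.

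The two pooled values are close although the underlying patterns are opposite.

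**6. What a between-cohort contrast can show.** SE = 9 × √(4/100 + 4/175) = 2.26 with all patients, and 2.26/√0.9 = 2.38 with 90% retained. Power for a 3.3-point difference in effect is 31% and 28% respectively. Reaching 80% power would need a difference of about 6.3 to 6.7 points.

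**The case against.** **The model may already be specified elsewhere.** Protocol 9.4.5 is in the contents but not in the text available, and the SAP's mITT and bITT definitions are not visible. A cohort term there cannot be excluded. This stands, and it makes the request conditional.

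**A reader might infer that a different effect by cohort would be concealed.** The documents do not support that. In the first example of step 5, the weak post-amendment result would be reported directly by that cohort's own MMRM, and the pre-amendment means would appear by arm. What is missing is a like-for-like, model-based comparison.

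**A reader might also infer that a positive bITT result could carry the mixed-features claim, or that the pooled estimate is biased.** Neither follows. The conclusion rests on mITT, bITT is a separate analysis outside the stated test sequence, and 1:1 allocation keeps cohort from confounding treatment.

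**The precision loss is trivial and conservative, and the contrast is weakly powered.** Both are true. They argue for an exploratory estimate with an interval and against any decision rule based on it.

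**The Table 9-1 mismatch is soft.** SAP 9.3 itself summarises a set outside the SAP 9 list (pre-amendment ITT patients), so that list is not strictly closed, and SAP Table 2-2 is not shown. The mismatch is therefore housekeeping.

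**Conclusion.** The point holds as a minor improvement to a supportive analysis. On the visible text, bITT combines two populations that the SAP itself distinguishes, in a set that is about 36% pre-amendment, and no model shown accounts for cohort. The cost in precision is small: roughly 1% to 4% on the SE for an assumed cohort difference of 3 to 5 points, or about 1 to 3 points of power from 82.2%, before any absorption by site and baseline. The more useful gain is interpretive: a stated effect in each cohort, and their difference with its uncertainty, beside the pooled figure.

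The size rests on the SD of 9, 10% dropout, 1:1 allocation in both periods, and assumed values of D. The finding itself rests on there being no bITT-specific model in the text not shown. No confirmatory conclusion of the trial depends on it.

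**What to change.** 1. Unless already specified, state in SAP 9 that the bITT MMRM includes cohort (before or after Amendment 2.0, by the protocol version in force at randomisation) and cohort-by-visit as fixed factors.
2. Report beside the pooled estimate the Day 43 treatment effect in each cohort and the difference between them with 95% CI. Take these from a separate model with treatment-by-cohort terms or from cohort-specific models, and label them exploratory.
3. Restrict that contrast to bipolar patients. MDD patients exist only after the amendment, so in an all-patients set it would mix cohort with diagnosis.
4. Housekeeping: add the all-patients efficacy analysis of Protocol Table 9-1 to the sets in SAP 9, or record its removal in SAP 15.

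**Cost.** With six post-baseline visits, cohort and cohort-by-visit add 1 + 5 = 6 parameters for about 275 patients. A separate heterogeneity model with treatment-by-cohort at each visit adds 6 more. Otherwise it takes a few sentences and about one table row, with no new data. Protocol 9 lets analysis changes be documented in the SAP without a protocol amendment; this should be done before unblinding.
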